3.0 PATIENT ELIGIBILITY

3.1 Inclusion Criteria:

Subjects must meet all of the inclusion criteria to participate in this study.

3.1.1 Ability to understand and the willingness to sign a written informed consent

3.1.2 Pathologically confirmed invasive breast cancer by core needle biopsy

3.1.3 Female subjects, age ≥ 18 years.

- 3.1.4** Only postmenopausal women will be eligible. Subjects will be classified as being postmenopausal if they have had:
- Bilateral surgical oophorectomy, or
 - No spontaneous menses > 1 year or
 - No menses for < 1 year with FSH and estradiol levels in postmenopausal range, according to institutional standards
- 3.1.5** Performance Status ECOG 0-2
- 3.1.6** Invasive breast cancer must be ER+ in ≥66 % of the cells or ER Allred score 6-8. If ER is positive in < 66%, the staining intensity (weak, intermediate, strong) is needed to calculate the Allred Score to determine eligibility. In institutions where ER expression is classified only by <1%, 1-10%, and >10% cut-offs, >10% expression is required for inclusion.
- 3.1.7** Invasive breast cancer must be HER2 negative. HER2 negative is defined as a single test or both tests used to determine HER2 status (ISH and IHC) show:
- IHC 1+ as defined by incomplete membrane staining that is faint/barely perceptible and within > 10% of the invasive tumor cells;
 - IHC 0 as defined by no staining observed or membrane staining that is incomplete and is faint/barely perceptible and within ≤ 10% of the invasive tumor cells
 - ISH single-probe average HER2 copy number < 4.0 signals/cell
 - ISH dual-probe HER2/CEP17 ratio < 2.0 with an average HER2 copy number < 4.0 signals/cell
- 3.1.8** Documentation of mammogram, ultrasound and MRI of the ipsilateral breast all performed within 42 days prior to registration.
- 3.1.9** Clinical T2-T4c, (by clinical measurement and/or breast imaging), any N, M0 invasive breast cancer, by AJCC 7th edition clinical staging, with the goal being surgery to complete excision of the tumor in the breast and the lymph node. For clinically node positive disease, any T is allowed. Palpable breast primary is not required.
- Note:
- Patients with contralateral invasive breast cancer are not eligible.
 - Patients with ipsilateral multifocal/multi-centric invasive breast cancer are eligible. The largest lesion will be evaluated for response assessment and calculation of PEPI score.
 - Patients with ductal carcinoma in situ in either breast are eligible.
- 3.1.10** Tissue acquisition: Subject must agree to provide the required research biopsies at baseline, at day 14 (+7 d) and at surgery for biomarker and correlative studies.
- 3.1.11** Subject has adequate bone marrow and organ function as defined by the following laboratory values at screening:
- Absolute neutrophil count ≥ 1500 /uL
 - Platelets ≥ 100,000 /uL
 - Hemoglobin ≥ 9.0 g/dL
 - Potassium, total calcium (corrected for serum albumin), magnesium, sodium and phosphorus within institutional upper limit of normal (IULN) or corrected to within normal limits with supplements before first dose of study medication.

(Supplements used for this purpose to be approved by PI). However, if the investigator believes the lab abnormalities are minor and clinically insignificant, the patient may be enrolled in the study.

- INR \leq 1.5
- Serum creatinine \leq 1.5 mg/dL or creatinine clearance \geq 50mL/min
- Alanine aminotransferase (ALT) and aspartate aminotransferase (AST) <2.5 x ULN.
- Total bilirubin \leq IULN; or total bilirubin \leq 3.0 x IULN or direct bilirubin \leq 1.5 ULN in patients with well documented Gilbert's Syndrome.

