12.3	ETHICS AND GOOD CLINICAL PRACTICE (GCP):	522
13.0	REGISTRATION PROCEDURES.....	522
13.1	GENERAL GUIDELINES FOR KUCC AND OTHER PARTICIPATING ORGANIZATIONS:	522
13.2	REGISTRATION PROCESS FOR KUCC AND OTHER PARTICIPATING CENTERS:	522
13.3	UNBLINDING:	533
14.0	STUDY MANAGEMENT	54
14.1	INVESTIGATOR FILES AND RETENTION OF DOCUMENTS:.....	544
14.2	CASE REPORT FORMS:.....	54
14.3	STUDY MONITORING:	54
15.0	STATISTICAL CONSIDERATIONS	54
15.1	STUDY DESIGN/STUDY ENDPOINTS:	544
16.0	SAMPLE SIZE JUSTIFICATION AND INTERIM ANALYSIS FOR FUTILITY	544
16.1	ACCRUAL RATE AND STUDY DURATION:	555
16.2	DATA ANALYSIS PLANS:.....	555
17.0	REFERENCES	566
18.0	APPENDICES.....	588

APPENDIX A: PERFORMANCE STATUS.....	588
APPENDIX B: LIST OF PROHIBITED MEDICATIONS DURING STUDY DRUG TREATMENT ⁵	599
APPENDIX C: LIST OF MEDICATIONS TO BE USED WITH CAUTION DURING STUDY DRUG TREATMENT.....	60
APPENDIX D: CONCOMITANT MEDICATIONS	611
APPENDIX E: CORRELATIVE STUDIES FOR THE FELINE TRIAL ([name]).....	622
APPENDIX F: DRUG COMPLIANCE ASSESSMENT TOOL (SAMPLE PARTICIPANT PILL DIARY).....	644

LIST OF ABBREVIATIONS

AE	Adverse Event
AI	Aromatase Inhibitor
AJCC	American Joint Committee on Cancer
ALT	Alanine Aminotransferase
ANC	Absolute Neutrophil Count
AST	Aspartate Aminotransferase
CBC	Complete Blood Count
cCR	Clinical Complete Response
CMP	Comprehensive Metabolic Panel
CTCAE	Common Terminology Criteria for Adverse Events
DFS	Disease Free Survival
DLT	Dose Limiting Toxicity
DSMC	Data and Safety Monitoring Committee
ECOG	Eastern Cooperative Oncology Group
EOT	End of Treatment
ER	Estrogen Receptor
hCG	Human Chorionic Gonadotropin
HER-2	ERBB2
IULN	Institutional Upper Limit of Normal
MRI	Magnetic Resonance Imaging
MTD	Maximum Tolerated Dose
pCR	Pathologic Complete Response
PD	Progressive Disease
PEPI	Pre-operative Endocrine Prognostic Index
PFS	Progression Free Survival
PO	per os/by mouth/orally
PR	Partial Response
RFS	Relapse Free Survival
RP2D	Recommended Phase 2 Dose
SAE	Serious Adverse Event
SD	Stable Disease
US	Ultrasound
WBC	White Blood Cells

Study Schema

- *Randomized to 3 capsules/d 3 weeks on/1week off or 2 capsules/d continuous dosing (see Section 4.1 for details)
- Research biopsies will be performed at baseline, at day 14 (+7d) and at surgery.
- A Ki67 value of >10% at day 14 biopsy will result in discontinuation of the protocol therapy since this is an early indicator of endocrine resistance.
- For the primary analysis, arms B and C will be combined vs arm A.

Study Summary

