3.2.3 An excisional biopsy of this breast cancer

3.2.4 Surgical axillary staging procedure prior to study entry.

Note: FNA or core needle biopsy of axillary node is permitted.

3.2.5 Hormone replacement therapy of any type, megestrol acetate, or raloxifene within four weeks prior to first study treatment.

3.2.6 Clinical or radiographic evidence of metastatic disease. Metastatic workup is not required.

Note: isolated ipsilateral supraclavicular node involvement is permitted

3.2.7 Treatment for this cancer including surgery, radiation therapy, chemotherapy, biotherapy, hormonal therapy or investigational agent prior to study entry.

3.2.8 History of invasive breast cancer prior to the current diagnosis.

3.2.9 Patient has a known hypersensitivity to any of the excipients of ribociclib or Letrozole.

3.2.10 Patient has a concurrent malignancy or malignancy within 3 years prior to starting study drug, with the exception of adequately treated, basal or squamous cell carcinoma, non-melanomatous skin cancer or curatively resected cervical cancer.

3.2.11 Patient has impairment of gastrointestinal (GI) function or GI disease that may significantly alter the absorption of the study drugs (e.g., ulcerative diseases, uncontrolled nausea, vomiting, diarrhea, malabsorption syndrome, or small bowel resection).

3.2.12 Patient has a known history of HIV infection (testing is not mandatory).

3.2.13 Patient has any other concurrent severe and/or uncontrolled medical conditions that would, in the investigator's judgment, cause unacceptable safety risks, contraindicate patient participation in the clinical study or compromise compliance with the protocol

(e.g. chronic pancreatitis, chronic active hepatitis, active untreated or uncontrolled fungal, bacterial or viral infections, etc.). Hepatitis testing at screening is not mandatory, but may be done per investigator discretion.

- 3.2.14** Patient has had major surgery within 14 days prior to starting study drug or has not recovered from major side effects (tumor biopsy is not considered a major surgery).
- 3.2.15** Patient with Child-Pugh score B or C
- 3.2.16** Patient has a history of non-compliance to medical regimen or inability to grant consent.
- 3.2.17** Patient is currently receiving or has received systemic corticosteroids ≤ 2 weeks prior to starting study drug, or who have not fully recovered from side effects of such treatment.

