- 3.2.18** Patient is currently receiving warfarin or other coumarin-derived anticoagulant for treatment, prophylaxis or otherwise. Therapy with heparin, low molecular weight heparin (LMWH) or fondaparinux is allowed
- 3.2.19** Clinically significant, uncontrolled heart disease and/or recent events including any of the following:
- History of acute coronary syndromes (including myocardial infarction, unstable angina, coronary artery bypass grafting, coronary angioplasty, or stenting) or symptomatic pericarditis within 12 months prior to screening.
 - History of documented congestive heart failure (New York Heart Association functional classification III-IV)
 - Documented cardiomyopathy
 - Patient has a Left Ventricular Ejection Fraction (LVEF) $< 50\%$ as determined by Multiple Gated acquisition (MUGA) scan or echocardiogram (ECHO) at screening
 - History of any cardiac arrhythmias, e.g., ventricular, supraventricular, nodal arrhythmias, or conduction abnormality within 12 months of screening
 - Congenital long QT syndrome or family history of long QT syndrome
 - Bradycardia (heart rate < 50 at rest), by ECG or pulse, at screening
 - Systolic blood pressure (SBP) > 160 mmHg or < 90 mmHg at screening.
- 3.2.20** On screening, inability to determine the QTcF interval on the ECG (i.e.: unreadable or not interpretable) or QTcF > 450 msec (using Fridericia's correction). All as determined by screening ECG.
- 3.2.21** Patient is currently receiving any of the following medications and cannot be discontinued 7 days prior to starting study drug (**APPENDIX B**):
- Known strong inducers or inhibitors of CYP3A4/5, including grapefruit, grapefruit hybrids, pomelos, star fruit, and Seville oranges
 - Those having a narrow therapeutic window and are predominantly metabolized through CYP3A4/5
 - Those having a known risk to prolong the QT interval or induce Torsades de Pointes
 - Herbal preparations/medications as listed in Appendix B

3.3 Staging Criteria:

Subjects will be staged prior to registration according to the clinical staging criteria adapted from the American Joint Committee on Cancer (AJCC) Cancer Staging Data Forms of the AJCC

Cancer Staging Manual, 7th Edition, 2009.

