4.5.5 Dose modification guidance in case of QT prolongation

Grade	Dose Modification
For all grades	
 • Check the quality of the ECG • Perform analysis of serum electrolytes (K⁺, Ca⁺⁺, Phos, Mg⁺⁺). If below the lower limit of normal, interrupt ribociclib administration, correct with supplements or appropriate therapy as soon as possible, and repeat electrolytes until documented as normal • Review concomitant medication usage for the potential to inhibit CYP3A4 and/or to prolong the QT interval • Check compliance with correct dose and administration of ribociclib
1	No dose adjustment required.

QTcF 450-480 ms	
2 QTcF 481-500 ms	
Interrupt ribociclib
 
Perform a repeat ECG one hour after the first QTcF of ≥ 481 ms
 
If QTcF < 481 ms, restart ribociclib at the same dose. No dose adjustment required for the first occurrence
 
 If QTcF remains ≥ 481 ms, repeat ECG as clinically indicated until the QTcF returns to < 481 ms. Restart ribociclib at the same dose level. No dose adjustments required for first occurrence. If QTcF ≥ 481 ms recurs, ribociclib should be reduced by 1 dose level (please refer to the dosing schedule table) 
Repeat ECGs 7 days and 14 days after dose resumption (then as clinically indicated) for any patient who has therapy interrupted due to QTcF ≥ 481 ms

3 QTcF ≥ 501 ms on at least two separate ECGs	
Interrupt ribociclib/placebo
 
 Consider consulting a local cardiologist Perform a repeat ECG one hour after the first QTcF of ≥ 501 ms. If QTcF remains ≥ 501 ms, repeat ECG as clinically indicated, but at least once a day until the QTcF returns to < 481 ms. If QTcF returns to < 481 ms, ribociclib/placebo should be reduced by 1 dose level (please refer to the dosing schedule table). 
Repeat ECGs 7 days and 14 days after dose resumption for any patient who has therapy interrupted due to QTcF ≥ 501 ms
 
 If QTcF of ≥ 501 ms recurs, discontinue ribociclib/placebo

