4 QT/QTcF ≥ 501 or > 60 ms change from baseline and Torsades de pointes or polymorphic ventricular tachycardia, or signs/symptoms of serious arrhythmia	
Discontinue ribociclib/placebo
 
 Obtain local cardiologist consultation Perform a repeat ECG one hour after the first QTcF of ≥ 501 ms 
If QTcF remains ≥ 501 ms, repeat ECG as clinically indicated, but at least once a day until the QTcF returns to < 501 ms.

4.5.6 Management of All Other Related Adverse Reactions:

Consider performing an analysis of serum potassium, calcium, phosphorus, and magnesium, for all adverse reactions that are potentially associated with electrolyte imbalance (e.g. diarrhea, nausea/vomiting). If the electrolyte values are below the lower limit of normal, interrupt ribociclib administration, correct electrolytes with supplements as soon as possible, and repeat electrolyte testing until documented normalization of the electrolytes.

4.6 Surgery:

4.6.1 Schedule: Surgery should be scheduled during days 8-22 of the 6th cycle of neoadjuvant endocrine therapy. Protocol therapy will be continued until the day before surgery.

Note: A surgical delay beyond the time frame described above, requires a discussion with the principal investigator or co-investigator. Given the subject population (older with co-morbid illnesses) it may be appropriate for a subject to remain on the endocrine agent to allow a delay in surgery to allow a recovery from inter-current illness for example. These issues will be dealt with on a case-by-case basis.

4.6.2 Breast surgery: The type of breast surgery (either mastectomy or lumpectomy) is determined by the treating surgeon according to institutional standard, with the goal to

completely excise the tumor. A negative margin is required unless further excision is not possible.

4.6.3 Lymph node surgery: The type of lymph node surgery (sentinel lymph node with or without axillary lymph node dissection) will be determined by the treating surgeon according to institutional standard.

4.6.4 Surgical pathology report: Size of the breast tumor; number of lymph nodes examined and the number of positive by H&E staining; final tumor margins; and extent of surgery should be reported with submission of surgical and pathology reports.

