13.0 REGISTRATION PROCEDURES

13.1 General Guidelines for KUCC and Other Participating Organizations:

Institutions will register eligible subjects through the KUCC Clinical Research Office central registration process. Registration must occur prior to the initiation of therapy. Any subject not registered to the protocol before treatment begins will be considered ineligible and registration will be denied.

The completed source documentation provided for eligibility verification and registration must be kept in the subject binder for monitoring purposes and documentation of subject eligibility.

Issues that would cause treatment delays should be discussed with the Principal Investigator. If a subject does not receive protocol therapy following registration, notify the KU Cancer Center Project Director or designee and change the subject's status in the eVELOS system.

13.2 Registration Process for KUCC and Other Participating Centers:

The Coordinating Center (KUCC), specifically the Project Director or designee is accessible for registration Monday through Friday from 8:00 AM to 5:00 PM Central Time.

The registration procedures are as follows:

1. Obtain written informed consent from the subject prior to the performance of any study related procedures or assessments.
2. Complete the appropriate baseline demographic information in eVELOS and the required registration form and inclusion/exclusion criteria checklist using the eligibility assessment documented in the subject's medical/research record. To be eligible for registration to the study, the subject must meet each inclusion and none of the exclusion criteria listed in Section 3.0 of this protocol. The KU department of biostatistics will grant access to eVelos for this study for access to study documents, patient enrollment and data entry into eCRFs.
3. Submit the registration form and inclusion/exclusion criteria checklist to KUMC via email. The KU Project Director or designee will send an email confirmation stating whether or not the subject may enroll.
4. The unblinded pharmacist or designee will assign the subject to a treatment group using sequential assignment of predetermined block randomized 1:1:1 treatment assignments provided by the study statistician prior to activation.

13.3 Unblinding:

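### The electrolyte entry criterion in 3.1.11 names only an upper limit, so read literally an uncorrected low value qualifies for a drug that can prolong QT

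*Combined protocol and SAP*

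**What the plan says.** The organ-function list in 3.1.11 covers potassium, albumin-corrected calcium, "magnesium, sodium and phosphorus within institutional upper limit of normal (IULN) or corrected to within normal limits with supplements before first dose". The principal investigator approves the supplements. A waiver follows: "if the investigator believes the lab abnormalities are minor and clinically insignificant, the patient may be enrolled in the study". The List of Abbreviations expands IULN as "Institutional Upper Limit of Normal".

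Section 1.5 lists QT prolongation among ribociclib's main adverse reactions. On treatment, 4.5.5 (QT prolongation) calls for potassium, calcium, phosphorus and magnesium to be measured: "If below the lower limit of normal, interrupt ribociclib administration, correct with supplements or appropriate therapy as soon as possible". Section 4.5.6 asks sites to consider testing the same four for related reactions that may involve electrolyte imbalance: "If the electrolyte values are below the lower limit of normal, interrupt ribociclib administration".

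Eligibility is confirmed centrally under 13.2: "To be eligible for registration to the study, the subject must meet each inclusion and none of the exclusion criteria listed in Section 3.0".

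**The concern.** A value below the lower limit of normal is also below the upper limit. Followed as printed, the criterion lets in a woman with low potassium, calcium, magnesium or phosphorus. She needs neither correction nor a judgment that the abnormality is minor, because on that reading nothing has to be corrected or waived. Central confirmation works from the Section 3.0 criteria, so it would not necessarily catch this.

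What is at stake is patient safety at entry. The protocol's own QT guidance treats a low value of these four electrolytes as a reason to stop ribociclib until it is corrected. The entry wording does not require that correction before the first dose.

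**Working it through.** The plan states no figure to reproduce. The check is a reading of the text.

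**Step 1: the criterion as printed (waiver aside).** Branch 1 is a value at or below the institutional upper limit. Branch 2 is a value corrected to normal with supplements. Either one suffices.

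| Screening value | Branch 1 as printed | Correction required? | Under normal limits (LLN to ULN) |
|---|---|---|---|
| Low | Met | No | Not met: correct, or apply the waiver |
| Normal | Met | No | Met |
| High | Not met | Yes, though supplements do not lower a high value | Not met: unchanged |

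On the literal reading branch 2 has almost no work to do: low values never reach it, and supplements do not bring down high ones. That is good evidence that normal limits were intended.

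**Step 2: is IULN used as a ceiling elsewhere?** Yes. The same list uses it as the maximum for total bilirubin. Where a floor is needed the list gives one: neutrophils at least 1500/uL, platelets at least 100,000/uL, haemoglobin at least 9.0 g/dL.

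**Step 3: each electrolyte across the document** (3.1.11, 4.5.5, 4.5.6, 5.0, 6.1.10, 6.4.5).

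| Electrolyte | Lower limit in branch 1 | Low value interrupts drug (4.5.5, 4.5.6) | Scheduled at screening | Scheduled day 1, cycles 2-6 |
|---|---|---|---|---|
| Potassium | No | Yes | Yes | Yes |
| Calcium | No | Yes | Yes | Yes |
| Magnesium | No | Yes | Yes | No |
| Phosphorus | No | Yes | Yes | No |
| Sodium | No | Not named | Yes | Yes |

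The counts are 0 of 5 with a lower limit at entry, 4 of 5 covered by the on-treatment rules, and 3 of 5 rechecked on schedule. Magnesium and phosphorus are the two that the on-treatment rules name but the calendar never schedules after screening. They would be measured again only if an event or a clinical decision prompted it.

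**Step 4: timing for the electrolytes that are rechecked.** The first scheduled chemistry and ECG on treatment fall on day 1 of cycle 2. With no holds that is 28 ± 3 days after first dose: 28 − 3 = 25 to 28 + 3 = 31 days.

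**Step 5: other entry criteria.** These were read for an electrolyte floor:
- 3.2.11: gastrointestinal disease that may alter absorption, including uncontrolled vomiting or diarrhea.
- 3.2.13: "concurrent severe and/or uncontrolled medical conditions that would" pose an unacceptable risk in the investigator's judgment.
- 3.2.19: cardiac disease, arrhythmia, long QT syndrome, bradycardia.
- 3.2.20: QTcF above 450 msec or not determinable.
- 3.2.21: drugs with a known QT risk.

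All narrow the group at risk. None sets a lower electrolyte limit.

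**The case against.** The strongest reply is that no competent site would read the bullet this way. Supplements exist to raise low values, and a waiver for minor abnormalities is pointless for low values that already pass. The intent is therefore plain. The fix also keeps the waiver, so minor low values would still enter. The only women affected are those with a low value of clinical importance who would be enrolled uncorrected, and 3.2.13 should stop the serious cases.

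Much of this stands. It supports calling the wording a slip and rating it minor. It does not make the printed threshold right: this is an operative entry limit, checked against the text of Section 3.0. With the fix, every low value must be either corrected or judged minor; as printed, neither is required.

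Stronger readings are tempting, and the documents do not support them:
- A reader might infer that the protocol chose to admit women with low electrolytes. The supplement clause points the other way.
- A reader might infer that entry contradicts a general floor on treatment. Sections 4.5.5 and 4.5.6 apply only after QT prolongation or a related adverse reaction, and 4.5.6 only suggests testing.
- A reader might extend the QT argument to sodium. Neither section names it.
- A reader might take the ribociclib doses swallowed before cycle 2 as a measure of risk. Dose totals do not measure QT risk.
- A reader might infer that women were harmed. The documents give no share with low values and no count of such enrolments.

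**Conclusion.** The concern holds as a wording error in an eligibility threshold, and it is minor. The missing lower limit affects all 5 electrolytes; the QT argument covers 4; and for 2 of those, magnesium and phosphorus, the entry criterion is the only scheduled check. The conclusion rests on the literal reading of the word joining the two branches and on IULN meaning what the abbreviation list says.

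No patient count can be given. Section 16.2 records accrual as almost complete by the time the first 60 patients had PEPI results, so the correction can help only women not yet enrolled, a number the documents do not state. Sample size, primary endpoint and analysis are unaffected.

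**What to change.** In 3.1.11, replace the reference to the upper limit with: *within institutional normal limits (LLN to ULN), or corrected to within those limits with supplements, with the corrected value documented before first dose*. Keep the investigator waiver for minor, clinically insignificant abnormalities.

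A matching conditional entry in the pre-treatment column of the Section 5.0 calendar would be convenient but is optional, since correction before first dose already implies a known repeat value.

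The cost is one phrase in an amendment, with IRB approval as 12.1 requires, plus an occasional repeat blood test and a short delay for the women affected. If the correction comes after randomization, the repeat has to fit the 14 days that 4.1 allows before treatment starts. If enrolment has already closed, nothing is gained in this trial.
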